Pneumonitis, grade 3/4	
 Permanently discontinue atezolizumab and cobimetinib.^c Refer patient to pulmonary and infectious disease specialists and consider bronchoscopy or BAL. If bronchoscopy is consistent with immune-related etiology, initiate treatment with 1–2 mg/kg/day oral prednisone or equivalent. If pulmonary event does not improve within 48 hr or worsens, consider adding an immunosuppressive agent (e.g., infliximab, cyclophosphamide, IV Ig, or mycophenolate mofetil). If event resolves to Grade 1 or better, taper corticosteroids over \geq 1 month.

BAL = bronchoscopic alveolar lavage.

^a If corticosteroids have been initiated, they must be tapered over \geq 1 month to \leq 10 mg/day oral prednisone or equivalent before atezolizumab can be resumed.

^b Atezolizumab may be withheld for a period of time beyond 12 weeks to allow for corticosteroids to be reduced to \leq 10 mg/day oral prednisone or equivalent. The acceptable length of the extended period of time must be agreed upon by the investigator and the Medical Monitor.

^c Resumption of atezolizumab may be considered in patients who are deriving benefit and have fully recovered from the immune-related event. Patients can be rechallenged with atezolizumab only after approval has been documented by both the investigator (or an appropriate delegate) and the Medical Monitor.

POTENTIAL EYE TOXICITY

An ophthalmologist should evaluate visual complaints.

Uveitis or episcleritis and other immune-mediated ocular disease may be associated with atezolizumab and may be treated with topical corticosteroid eye drops. Atezolizumab should be permanently discontinued for immune-mediated ocular disease that is unresponsive to local immunosuppressive therapy.

Serous retinopathy have been associated with cobimetinib.

Potential ocular toxicity should be managed according to the guidelines in [Table A3-5](#).

Event	Action to Be Taken
Ocular toxicity	
Serous retinopathy Severity grade assessment based on NCI CTCAE v4 "Eye Disorders – Other" scale ^{d, e, f, g}	
Serous retinopathy, Grade 1^d or 2^e (tolerable):
 
 Continue cobimetinib and atezolizumab without dose change. Continue ophthalmology follow-up as clinically indicated. 
Serous retinopathy, Grade 2^e (intolerable) or 3/4^{f/g}:
 
 Interrupt cobimetinib until grade ≤1. Continue atezolizumab as clinically indicated. Consult ophthalmology and undergo complete ophthalmologic examination, which includes visual acuity testing, intra-ocular pressure measurements, slit lamp ophthalmoscopy, indirect ophthalmoscopy, visual field, and OCT. Consider a fluorescein angiogram and/or indocyanine green angiogram, if clinically indicated. Cobimetinib should be dose reduced by 1 dose level when restarting. Consider permanent discontinuation of cobimetinib if serous retinopathy recurs despite 2 dose level reductions
Potential immune-related ocular toxicity (e.g., uveitis, iritis, episcleritis, or retinitis)	
 Follow guidelines provided in the Atezolizumab Investigator's Brochure. Continue cobimetinib as clinically indicated.
Retinal vein occlusion (any grade)	
 If RVO (any grade) is diagnosed, cobimetinib dosing should be permanently discontinued and RVO treated per institutional guidelines. Continue atezolizumab.

ADL=activities of daily living; NCI CTCAE=National Cancer Institute Common Terminology Criteria for Adverse Events; RVO=retinal vein occlusion; OCT=optical coherence tomography.

^d Grade 1: Asymptomatic or mild symptoms; clinical or diagnostic observations only; intervention not indicated.

^e Grade 2: Moderate; minimal, local or noninvasive intervention indicated; limiting age appropriate instrumental ADL.

^f Grade 3: Severe or medically significant but not immediately sight threatening; hospitalization or prolongation of existing hospitalization indicated; disabling; limiting self-care ADL.

^g Grade 4: Sight-threatening consequences; urgent intervention indicated; blindness (20/200 or worse) in the affected eye.

GUIDELINES FOR MANAGEMENT OF PATIENTS WHO EXPERIENCE DECREASED LEFT VENTRICULAR EJECTION FRACTION

Decreased LVEF has been seen with cobimetinib (See Section 5.1.1.1) Refer to

Table A3-6. Permanent discontinuation of cobimetinib treatment should be considered if cardiac symptoms are attributed to cobimetinib and do not improve after temporary interruption.

Left Ventricular Ejection Fraction (LVEF) Decrease From Baseline				
Patient	LVEF value	Recommended action with cobimetinib and atezolizumab	LVEF value following treatment break	Recommended cobimetinib daily dose
Asymptomatic	≥50% (or 40%–49% and <10% absolute decrease from BL)	Continue atezolizumab and cobimetinib at current dose	N/A	N/A
	<40% (or 40%–49% and ≥10% absolute decrease from BL)	Interrupt cobimetinib treatment for 2 wk Continue atezolizumab as clinically indicated	<10% absolute decrease from BL	First occurrence: 40 mg
				Second occurrence: 20 mg
				Third occurrence: permanent discontinuation
Symptomatic	N/A		Asymptomatic and <10% absolute decrease from BL	First occurrence: 40 mg
				Second occurrence: 20 mg
				Third occurrence: Permanent discontinuation
			Asymptomatic and <40% (or ≥10% absolute decrease from BL)	Permanent discontinuation

		
Interrupt cobimetinib treatment for 4 wk.
 
Consider withholding atezolizumab
 
Discuss with Medical Monitor regarding resumption of atezolizumab.
 
Cardiology consultation is strongly recommended.
	
Symptomatic regardless of LVEF
	
Permanent discontinuation

--	--	---	---------------------------------------	----------------------------------

BL=baseline; LVEF=left ventricular ejection fraction; N/A=not applicable.

GUIDELINES FOR MANAGEMENT OF PATIENTS WHO EXPERIENCE ELEVATED CPK

Elevated CPK has been reported with cobimetinib (see Section 6.1.2.5). See [Table A3-7](#).

Table A3-7 Recommended Dose Modifications for Cobimetinib in Patients with CPK Elevations

Event	Action to Be Taken
Rhabdomyolysis or CPK elevation	
General guidance	
 Rule out cardiac cause (check ECG, serum cardiac troponin, and CPK-isoforms M and B fraction) and rule out rhabdomyolysis (clinical examination; serum creatinine, potassium, calcium, phosphorus, uric acid, and albumin; and urine myoglobin). Assess patient for any history of strenuous physical activity, blunt trauma, or recent IM injections.
Asymptomatic CPK elevation, Grade 1, 2, or 3	
 Continue atezolizumab and cobimetinib. Recheck CPK at least once a week.
Asymptomatic CPK elevation, Grade 4	
 Withhold cobimetinib and atezolizumab treatment. If improved to Grade \leq 3 within 4 weeks, restart cobimetinib at a dose reduced by 20 mg, if clinically indicated. If not, permanently discontinue cobimetinib. Resumption of atezolizumab may be considered in patients who are deriving benefit.
Rhabdomyolysis or symptomatic CPK elevations	
 Withhold cobimetinib and atezolizumab treatment. If event improves by at least one grade and symptoms resolve within 4 weeks, restart cobimetinib at a dose reduced by 20 mg, if clinically indicated. If not, permanently discontinue cobimetinib. Resumption of atezolizumab may be considered in patients who are deriving benefit after discussion with the Medical Monitor.
Hemorrhage	
Grade 3 hemorrhage other than cerebral hemorrhage	
 Withhold cobimetinib. Continue atezolizumab. Clinical judgment should be applied when considering whether cobimetinib should be resumed. There are no data on the effectiveness of cobimetinib dose modification for hemorrhage events. If cobimetinib cannot be resumed within 28 days, permanently discontinue cobimetinib.
Grade 4 hemorrhage or any grade cerebral hemorrhage	
 Permanently discontinue cobimetinib if the event is attributed to cobimetinib; otherwise, withhold cobimetinib. Continue atezolizumab. Clinical judgment should be applied when considering whether cobimetinib should be resumed. There are no data on the effectiveness of cobimetinib dose modification for hemorrhage events.

CPK = creatine phosphokinase.

Event	Action to Be Taken
Grade 3 or 4 or intolerable	
 Withhold atezolizumab and cobimetinib.
Grade 2 treatment-related toxicities not described above	
 If event resolves to Grade 1 or better within 12 weeks, resume atezolizumab at fixed dose. If not, permanently discontinue atezolizumab. ^{a,b,c} If event resolves to Grade 1 or better within 28 days, resume cobimetinib with dose reduced by one level. If not, permanently discontinue cobimetinib.

^a If corticosteroids have been initiated, they must be tapered over \geq 1 month to \leq 10 mg/day oral prednisone or equivalent before atezolizumab can be resumed.

^b Atezolizumab may be withheld for a period of time beyond 12 weeks to allow for corticosteroids to be reduced to \leq 10 mg/day oral prednisone or equivalent. The acceptable length of the extended period of time must be agreed upon by the investigator and the Medical Monitor.

^c Resumption of atezolizumab may be considered in patients who are deriving benefit and have fully recovered from the immune-related event. Patients can be rechallenged with atezolizumab only after approval has been documented by both the investigator (or an appropriate delegate) and the Medical Monitor.

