5.5.1 Dose Modifications for Cobimetinib

NOTE: Investigators can interrupt dosing of atezolizumab (or cobimetinib) depending on the attribution of the toxicity, which is at the discretion of the investigator. During this time, treatment may continue with the other non-attributable treatment agent.

NOTE: If either atezolizumab or cobimetinib are discontinued, dosing with the other drug may continue at the discretion of the investigator.

NOTE: For Grade ≥ 3 toxicities associated primarily with laboratory abnormalities only, study treatment may continue without interruption and/or dose reduction at the discretion of the investigator per institutional practice.

Table 2: Recommended Cobimetinib Dose Modifications

Grade (CTCAE)	Recommended dose modification
Grade 1 or Grade 2 (tolerable)	No dose reduction. Maintain cobimetinib at the same dose of 60 mg QD (3 tablets)
Grade 2 (intolerable) or Grade 3 or 4 (any)*	
First appearance	Interrupt treatment until Grade ≤ 1 , restart treatment at 40 mg QD (2 tablets)
Second appearance	Interrupt treatment until Grade ≤ 1 , restart treatment at 20 mg QD (1 tablet)
Third appearance	Consider permanent discontinuation

* If cobimetinib is withheld for > 28 days because of toxicity, the patient should be discontinued from cobimetinib, unless resumption of treatment is approved by the Medical Monitor after discussion with the investigator.

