5.5.3 Specific Dose Modifications for atezolizumab

Toxicities associated or possibly associated with atezolizumab treatment should be managed according to standard medical practice. Additional tests, such as autoimmune serology or biopsies, may be used to determine a possible immunogenic etiology. Although most immune-mediated adverse events observed with immunomodulatory agents have been mild and self-limiting, such events should be recognized early and treated promptly to avoid potential major complications. Discontinuation of atezolizumab may not have immediate therapeutic effect, and in severe cases, immune-mediated toxicities may be acutely managed with topical corticosteroids, systemic corticosteroids, or other immunosuppressive agents.

The primary approach to Grade 1 and 2 immune-mediated adverse events is supportive and symptomatic care with continued treatment with atezolizumab; for higher grade immune-mediated adverse events, atezolizumab should be withheld and oral/parenteral steroids administered. Recurrent Grade 2 immune-mediated adverse events may also mandate withholding atezolizumab or the use of steroids. Consideration for benefit-risk balance should be made by the investigator, with consideration of the totality of information as it pertains to the nature of the toxicity and the degree of clinical benefit a given patient may be experiencing prior to further administration of atezolizumab.

Atezolizumab should be permanently discontinued in patients with life-threatening immune-mediated adverse events. Patients who discontinue atezolizumab treatment may still remain in the study until loss of clinical benefit. Management of systemic immune activation is presented below.

See the atezolizumab Investigator's Brochure and Appendix 7 for details on management of gastrointestinal, dermatologic, endocrine, pulmonary toxicity, hepatotoxicity, potential pancreatic or eye toxicity and other immune-mediated adverse events. See Appendix 8 for precautions for anaphylaxis.

Systemic Immune Activation

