Dermatologic event, Grade 1/2	
 Continue atezolizumab and cobimetinib. Initiate supportive care (e.g., antihistamines, topical corticosteroids). If event does not improve, consider treatment with higher-potency topical corticosteroids. For grade 2 rash, consider referral to dermatologist. 
Acneiform rash:
 
 Consider topical corticosteroids (e.g., hydrocortisone 2.5%, alclometasone) and oral antibiotics (minocycline, doxycycline, or antibiotics covering skin flora) as clinically indicated.
Dermatologic event, Grade 3	
 Withhold atezolizumab and cobimetinib. Refer patient to dermatologist. A biopsy should be performed if appropriate. Consider initiating treatment with 10 mg/day oral prednisone or equivalent, increasing dose to 1–2 mg/kg/day if event does not improve within 48–72 hours. If event resolves to Grade 2 or better within 12 weeks, resume atezolizumab at fixed dose. If not, permanently discontinue atezolizumab and cobimetinib.^{a,b} Permanently discontinue atezolizumab and cobimetinib and contact Medical Monitor if event does not resolve to Grade 1 or better within 12 weeks.^{a, b, c} If event resolves to Grade 2 or better within 28 days, resume cobimetinib with dose reduced by one level. If not, permanently discontinue cobimetinib. 
Acneiform rash:
 
 Consider continuation of topical corticosteroids (e.g., hydrocortisone 2.5% alclometasone) and oral antibiotics (e.g., minocycline, doxycycline or antibiotics covering skin flora) when restarting cobimetinib.
Dermatologic event, Grade 4	
 Permanently discontinue atezolizumab and cobimetinib, and contact Medical Monitor.^c

^a If corticosteroids have been initiated, they must be tapered over ≥ 1 month to ≤ 10 mg/day oral prednisone or equivalent before atezolizumab can be resumed.

^b Atezolizumab may be withheld for a period of time beyond 12 weeks to allow for corticosteroids to be reduced to ≤ 10 mg/day oral prednisone or equivalent. The acceptable length of the extended period of time must be agreed upon by the investigator and the Medical Monitor.

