^c Resumption of atezolizumab may be considered in patients who are deriving benefit and have fully recovered from the immune-related event. Patients can be rechallenged with atezolizumab only after approval has been documented by both the investigator (or an appropriate delegate) and the Medical Monitor.

PULMONARY TOXICITY

Mild-to-moderate events of pneumonitis have been reported with atezolizumab and cobimetinib. All pulmonary events should be thoroughly evaluated for other commonly reported etiologies such as pneumonia/infection, lymphangitic carcinomatosis, pulmonary embolism, heart failure, chronic obstructive pulmonary disease, or pulmonary hypertension:

- Measurement of oxygen saturation (i.e., arterial blood gas)
- High-resolution computed tomography (CT) scan of the chest
- Bronchoscopy with bronchoalveolar lavage and biopsy (if clinically feasible)
- Pulmonary function tests (diffusion capacity of the lung for carbon monoxide)
- Pulmonary function testing with a pulmonary embolism protocol

Patients will be assessed for pulmonary signs and symptoms throughout the study. Patients will also have CT scans of the chest at every tumor assessment.

Pulmonary toxicity should be managed according to the guidelines in [Table A3-4](#).

Table A3-4 Guidelines for Managing Atezolizumab- and Cobimetinib-Associated Pulmonary Toxicity

Pulmonary events	
Pneumonitis, grade 1	
 • Continue atezolizumab and cobimetinib. • Re-evaluate on serial imaging. • Consider patient referral to pulmonary specialist. • For recurrent pneumonitis, treat as Grade 3 or 4 event.

Pneumonitis, grade 2	
 Withhold atezolizumab and cobimetinib. Refer patient to pulmonary and infectious disease specialists and consider bronchoscopy or BAL. If bronchoscopy is consistent with immune-related etiology, initiate treatment with 1–2 mg/kg/day oral prednisone or equivalent. Resume atezolizumab and cobimetinib if event resolves to Grade 1 or better within 12 weeks.^{a, b} Permanently discontinue atezolizumab and cobimetinib and contact Medical Monitor if event does not resolve to Grade 1 or better within 12 weeks.^{a, b, c} For recurrent events, treat as a Grade 3 or 4 event.

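### Appendix 6, Table A3-3, Grade 3 dermatologic event: two grade thresholds for one atezolizumab decision, so a rash first reaching Grade 2 at about week 12 is told both to resume and to stop

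*Combined protocol and SAP*

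**What the plan says.** The Grade 3 row of Table A3-3 withholds both drugs and then gives three rules on restarting and stopping:

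- **First 12-week bullet** (footnotes a and b): "If event resolves to Grade 2 or better within 12 weeks, resume atezolizumab at fixed dose". Its 'If not' clause permanently stops both drugs.
- **Second 12-week bullet** (footnotes a, b and c): "Permanently discontinue atezolizumab and cobimetinib and contact Medical Monitor if event does not resolve to Grade 1 or better within 12 weeks".
- **Cobimetinib bullet**: "If event resolves to Grade 2 or better within 28 days, resume cobimetinib with dose reduced by one level". Its 'If not' clause permanently stops cobimetinib.

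The Grade 1/2 row of the same table continues both drugs with supportive care.

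The general rules use a lower grade. Table 3 (Section 5.5.2) restarts atezolizumab after a Grade 3 or 4 event only at Grade 1 or lower. Table 2 (Section 5.5.1) requires Grade 1 or lower before cobimetinib restarts. Section 5.5.4 requires baseline or Grade 1 or lower.

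**The concern.** The two 12-week bullets answer the same question, whether atezolizumab may be given again, over the same period but at different grades. A patient whose rash has come down to Grade 2 meets the first bullet's condition for resuming and also the second bullet's condition for permanent discontinuation.

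For a patient who first reaches Grade 2 near week 12, cobimetinib has already been stopped. Section 5.5.1 allows the other drug to go on: "If either atezolizumab or cobimetinib are discontinued, dosing with the other drug may continue at the discretion of the investigator". The atezolizumab decision therefore settles whether this patient stays on any study treatment. Two investigators could follow the same table cell and act in opposite ways.

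**Working it through.** The plan states no figure on this point, so the check is mainly one of logic.

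**Step 1. Put each possible grade at week 12 through the two bullets.**

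| Grade at week 12 | First bullet | Second bullet | Result |
|---|---|---|---|
| 0 or 1 | resume atezolizumab | not triggered | consistent |
| 2 | resume atezolizumab | stop permanently | opposite |
| 3 | stop permanently | stop permanently | consistent |

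**Step 2. Separate patients by when they reach Grade 2.**

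- *First at Grade 2 at about week 12.* Both bullets apply at once and cannot both be obeyed. Grade 2 was not reached by day 28, so the cobimetinib bullet has already stopped cobimetinib. Only atezolizumab is in dispute.
- *At Grade 2 earlier.* The bullets could be followed in order: resume on reaching Grade 2, then stop at week 12 if the rash is still above Grade 1. The text does not say this. It would also make the first bullet's 'If not' stop redundant, since every event worse than Grade 2 at week 12 is also worse than Grade 1.
- *At Grade 2 by day 28, cobimetinib restarted.* If the rash is unchanged at week 12, the second bullet stops cobimetinib, 84 − 28 = 56 days after a restart on day 28 (both periods counted from the same hold date, an assumption). The two rules act at different times.

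**Step 3. Look for a tie-breaker.**

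- Footnote a concerns steroid taper, and footnote b a longer atezolizumab hold for that taper. Neither sets a grade.
- Footnote c says "Resumption of atezolizumab may be considered in patients who are deriving benefit and have fully recovered from the immune-related event". A residual Grade 2 rash is not full recovery.
- Sections 5.5.2 and 5.5.4 send specific events to the management appendix, and 5.5.4 names rash. (They cite Appendix 7; the guidance is in Appendix 6.) The dermatologic text of Appendix 6 then sends rash to Table A3-3, so the general rules hand the question back to the cell that contains the conflict.

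**Step 4. Compare other rows of Appendix 6.** The Grade 2 hepatic and Grade 2 pneumonitis rows use Grade 1 in both the resume and the stop bullet. The pneumonitis stop bullet has the same wording as the second bullet here. In the diarrhea and colitis rows that allow a restart, both drugs restart at Grade 1. The catch-all row also uses one grade: "If event resolves to Grade 1 or better within 12 weeks, resume atezolizumab at fixed dose. If not, permanently discontinue atezolizumab". This suggests, without proving, that the second bullet was carried over from a row with a Grade 1 restart.

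**Step 5. Size.** Section 2.7 reports Grade 3 or higher rash in 4.4% of 90 patients, that is 4/90.

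- Exact 95% CI for 4/90: 1.2% to 11.0%.
- Expected here: 60 × 4/90 = 2.7 patients (60 × CI limits: 0.7 to 6.6).
- The documents do not say how many such events sit at Grade 2 at week 12. Assumed fractions of 10%, 25% and 50% give 2.67 × 0.10 = 0.3, 2.67 × 0.25 = 0.7 and 2.67 × 0.50 = 1.3 patients. Across the CI limits as well, the range is 0.07 to 3.3.
- These counts include patients who reached Grade 2 earlier. The group with an unavoidable clash is a subset of them.

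**The case against.** The strongest reply is that the protocol already leans one way. Tables 2 and 3 and Section 5.5.4 all use Grade 1 or lower, which agrees with the second bullet. That bullet requires Medical Monitor contact, Section 5.5 preserves clinical judgment, and Section 5.5.3 adds "Consideration for benefit-risk balance should be made by the investigator". On this view a cautious investigator would stop, and someone is always available to decide.

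Much of this stands. The general rules do favor the stricter bullet, and there is a decision-maker. But naming who decides does not name the grade, and the row departs from the general rules in two places: the first bullet and the cobimetinib bullet both restart at Grade 2. A default that the row has set aside twice cannot be presumed to govern the third rule.

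The sequential reading also has force. It removes the direct clash for patients who reach Grade 2 well before week 12, though the text would have to state it. It does nothing for a patient who first reaches Grade 2 at week 12.

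A reader might further infer that the second bullet contradicts the cobimetinib bullet. It does not. One acts within 28 days and the other at 12 weeks, and both can be obeyed. Stopping cobimetinib for a rash no worse than when it was restarted sits oddly with the earlier rule, but no date carries opposite cobimetinib orders.

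**Conclusion.** Wrong as written, for a narrow group. The row sets two thresholds for one atezolizumab decision, and for an event first reaching Grade 2 at about week 12 the instructions cannot be reconciled from the documents.

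Two larger claims are not supported. A reader might infer that the conflict decides between keeping and losing both drugs. In the group with the unavoidable clash, cobimetinib has already gone under its own 28-day rule. A reader might also take the 0.3 to 1.3 patients as the number in that group. They are ceilings under assumed fractions.

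The scale rests on carrying the Phase Ib rate over to these cohorts. That rate is only a guide: it covers the single term rash and includes any Grade 4 events, which fall in another row.

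The sample size calculation in Section 5.10.3 does not depend on the restart rule, so power and alpha are unchanged. Grade 3 or higher rash already counts as a toxicity event in Section 5.10.5, whichever bullet is followed. The matter is treatment continuation for very few patients, and it merits a correction because the repair is simple.

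**What to change.** State one atezolizumab threshold in the row.

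**Preferred: Grade 2.** This agrees with the first bullet, with the cobimetinib bullet and with the Grade 1/2 row that continues both drugs. Delete the Grade 1 stop bullet. Move its Medical Monitor contact and footnote c into the first bullet's 'If not' clause. Label the row an event-specific exception to Tables 2 and 3 and Section 5.5.4. The cost is an explicit departure from the general restart rule and the loss of the week-12 stop for a rash that stays at Grade 2.

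**Alternative: Grade 1.** If the clinical team prefers the stricter rule, change the resume threshold in the first bullet to Grade 1 or better and set the cobimetinib bullet to Grade 1 as well, so that the row matches the diarrhea and colitis rows. The cost is that some patients with residual Grade 2 rash lose treatment.

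Either choice changes one table cell, plus the exception label if Grade 2 is chosen, and can wait for the next amendment.

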5.5.4 Specific Dose Modifications for cobimetinib

Withhold cobimetinib for NCI CTCAE intolerable Grade ≥ 2 toxicity.

When restarting therapy after withholding treatment for a toxicity that has resolved to baseline or grade ≤ 1 :

- Reduce cobimetinib dose to 40 mg
- Reduce cobimetinib to 20 mg for second appearance of intolerable Grade ≥ 2 toxicity.
- Permanently discontinue cobimetinib on third appearance of intolerable Grade ≥ 2 toxicity unless the benefits for the individual patient are deemed to outweigh the risks.

For detailed recommendations regarding management of certain AEs, i.e. gastrointestinal toxicity (diarrhea), hepatotoxicity, rash, pulmonary toxicity, eye toxicity and cardiotoxicity, see Appendix 7.

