6.1.2.2 Left Ventricular Dysfunction

Decrease from baseline in left ventricular ejection fraction has been reported in patients receiving cobimetinib. Decreased left ventricular ejection fraction may be symptomatic or asymptomatic.

All patients will undergo evaluation of left ventricular ejection fraction, either by echocardiography or multigated acquisition scan at baseline, at specified timepoints during treatment, at the end of treatment, and as clinically indicated.

Guidelines for management of patients who have decreases in left ventricular ejection fraction are provided in Appendix 7.

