Appendix 6 Management of Cobimetinib plus Atezolizumab-Associated Adverse Events

Guidelines for Management of Patients Who Experience Specific Adverse Events

Event	Action to Be Taken
General guidance for dose modifications and treatment delays and discontinuation	
 There will be no dose modifications for atezolizumab. If atezolizumab is withheld and corticosteroids are initiated for an atezolizumab-related toxicity, corticosteroids must be tapered over ≥ 1 month to ≤ 10 mg/day oral prednisone or equivalent before atezolizumab can be resumed.^{a, b, c} The dose of cobimetinib can be reduced by 20 mg (one dose level) up to two times (i.e., from 60 mg to 40 mg and then from 40 mg to 20 mg). If further dose reduction is indicated after two dose reductions, the patient must discontinue cobimetinib but may continue treatment with atezolizumab at the investigator's discretion. If cobimetinib is withheld for > 28 days because of toxicity, the patient should be discontinued from cobimetinib, unless resumption of treatment is approved by the Medical Monitor after discussion with the investigator.
IRRs, anaphylaxis, and hypersensitivity reaction	
 Guidelines for management of IRRs are provided in the Atezolizumab Investigator's Brochure for atezolizumab. For anaphylaxis precautions, see Appendix 8. For severe hypersensitivity reactions, permanently discontinue all study treatment.

IRR=infusion-related reaction.

^a If corticosteroids have been initiated, they must be tapered over ≥ 1 month to ≤ 10 mg/day oral prednisone or equivalent before atezolizumab can be resumed.

^b Atezolizumab may be withheld for a period of time beyond 12 weeks to allow for corticosteroids to be reduced to ≤ 10 mg/day oral prednisone or equivalent.

The acceptable length of the extended period of time must be agreed upon by the investigator and the Medical Monitor.

^c Resumption of atezolizumab may be considered in patients who are deriving benefit and have fully recovered from the immune-related event. Patients can be rechallenged with atezolizumab only after approval has been documented by both the investigator (or an appropriate delegate) and the Medical Monitor.

GASTROINTESTINAL TOXICITY

Diarrhea and colitis have been associated with the administration of cobimetinib plus atezolizumab.

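### The Appendix 6 LVEF table gives cobimetinib restart doses in fixed mg, so read literally a patient already at 20 mg is listed to restart at 40 mg after a first LVEF event

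*Combined protocol and SAP*

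**What the plan says.** Section 6.1.2.2 describes the risk: "Decrease from baseline in left ventricular ejection fraction has been reported in patients receiving cobimetinib". For management it says "Guidelines for management of patients who have decreases in left ventricular ejection fraction are provided in Appendix 7". Section 5.5.4 likewise directs the reader for "eye toxicity and cardiotoxicity, see Appendix 7". The guidance is in fact printed as Appendix 6; Appendix 7 covers anaphylaxis.

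In the LVEF table of that appendix, the last column is headed "Recommended cobimetinib daily dose". Two rows cover patients who may restart: asymptomatic patients whose LVEF has recovered to within 10 percentage points of baseline, and symptomatic patients who have become asymptomatic with the same recovery. Both carry the same ladder: "First occurrence: 40 mg", 20 mg at the second occurrence, permanent discontinuation at the third. Neither row mentions the dose the patient was taking.

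The general guidance at the head of the appendix is written relative to the current dose: "The dose of cobimetinib can be reduced by 20 mg (one dose level) up to two times", with the steps given as 60 to 40 mg and 40 to 20 mg. It continues: "If further dose reduction is indicated after two dose reductions, the patient must discontinue cobimetinib", while atezolizumab may go on at the investigator's discretion.

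**The concern.** The table counts LVEF occurrences and attaches a fixed dose to each count. That works if every earlier reduction was for LVEF. It need not be so: Section 5.5.1 Table 2 takes a patient to 20 mg after a second qualifying toxicity of any kind. Section 5.6.7 schedules echocardiograms at Cycle 2, at Cycles 5, 8 and 11, and every four cycles from Cycle 15, and Section 4.1 expects about 12 months of therapy. A first LVEF event can therefore be found after earlier reductions for something else.

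For such a patient, the text that the protocol relies on for a known cardiac risk of cobimetinib lists a higher dose after a cardiac event than before it. What is at stake is the correctness of a safety instruction for an uncommon type of patient. No efficacy analysis depends on it.

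**Working it through.** The plan states no figure to reproduce. The check is to list the states in which an LVEF event can occur and compare the table's restart dose with the dose at the event.

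**Inputs.** Starting dose 60 mg (Section 5.3). Table ladder 40 mg, 20 mg, stop (Appendix 6, LVEF table). General guidance: 20 mg steps, at most two, then stop if a further reduction is indicated (Appendix 6).

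**Assumption.** Each other toxicity (O) lowers the dose by one level, or stops the drug if the patient is already at 20 mg. After each LVEF event (L) the table is followed and LVEF is taken to recover.

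**Formula.** Change = restart dose in the table − dose at the event.

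| Sequence | LVEF event | Dose at event | Table restart | Change |
|---|---|---|---|---|
| L | 1st | 60 mg | 40 mg | 40 − 60 = −20 mg |
| O, L | 1st | 40 mg | 40 mg | 40 − 40 = 0 |
| O, O, L | 1st | 20 mg | 40 mg | 40 − 20 = +20 mg (40/20 = 2, doubled) |
| L, L or O, L, L | 2nd | 40 mg | 20 mg | 20 − 40 = −20 mg |
| L, O, L | 2nd | 20 mg | 20 mg | 20 − 20 = 0 |
| L, L, L | 3rd | 20 mg | stop | stop |

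Three states give a one-level reduction or a stop, two leave the dose unchanged, and one doubles it (3 + 2 + 1 = 6).

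**Against the general guidance.**
- The three step-down or stop states agree with it.
- The two unchanged states do not breach it. The guidance is permissive about reducing, and its requirement to stop applies only if a further reduction is indicated.
- The state at 20 mg cannot be reconciled with it. At its strictest the guidance leads to discontinuation; at its most permissive it leaves the patient at 20 mg. No reading of it gives 40 mg.

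**Against the rest of the appendix.** Several rows word the restart relative to the current dose, for example serous retinopathy: "Cobimetinib should be dose reduced by 1 dose level when restarting". Diarrhea, colitis, Grade 3 rash, CPK elevation and the catch-all row do the same. Not every row steps down: Grade 2 pneumonitis resumes with no stated reduction, and resumption after hemorrhage is left to judgment. So the appendix has no uniform step-down rule, but no other row lists a dose that could exceed the current one.

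**The case against.** The best case against is that the table should not be read alone. Section 5.5.4, which refers the reader to the appendix for cardiotoxicity, gives the same ladder of 40 mg, 20 mg and discontinuation, and words the first two steps as reductions. One cannot reduce from 20 mg to 40 mg, so on a joint reading 40 mg is simply the first step down from 60 mg. If the appearances in Section 5.5.1 Table 2 are counted across toxicities, a patient already at 20 mg is at the third appearance, where stopping is to be considered. The column heading makes the doses recommendations, and Section 5.5 keeps the investigator's clinical judgment in place.

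Much of this stands. It shows that the doubling is almost certainly unintended and that an attentive investigator would not follow it. It does not remove the defect. Section 5.5.4 covers intolerable toxicity of Grade 2 or above and may not reach every asymptomatic LVEF fall. The table counts LVEF occurrences only and carries no footnote. Nothing states an order of precedence. The strong recommendation of a cardiology consultation sits in the symptomatic row, not the asymptomatic one.

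Three stronger readings are tempting and not supported. A reader might infer that the protocol forbids re-escalation and the table breaks that ban; the documents contain no such ban, only an absence of any provision for it. A reader might count the two unchanged-dose states as contradictions; the permissive and conditional wording of the general guidance does not bear that out. A reader might also infer that patients will in fact be given a doubled dose; that ignores the recommended status of the doses and the reliance on judgment.

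**Conclusion.** Minor, but wrong as written. In one of the six states, a first LVEF event in a patient already at 20 mg, the table followed literally gives 40 mg, an increase of 20 mg or 100%. No other text in the protocol supports that dose, and none expressly overrides it.

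The conclusion assumes that an occurrence in the table means an LVEF occurrence, as its title implies, and that the patient's LVEF recovers enough to qualify for restart. The six states are not weighted by likelihood. The documents give no rate for LVEF events or for dose reductions, so the number of the 60 planned patients who could be affected cannot be estimated. The affected state needs two earlier non-cardiac reductions, then a qualifying LVEF event, then recovery. Actual harm is unlikely. There is no effect on the primary endpoint, power, error rate or sample size.

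**What to change.** Add to both recovered rows of the LVEF table: *The restart dose must not exceed the dose at the time of the event; for a patient already at 20 mg, apply the general guidance of this appendix (discontinue if a further reduction is indicated).*

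A first event at 60 mg still restarts at 40 mg, one at 40 mg still restarts at 40 mg, and one at 20 mg leads to at most 20 mg or to stopping. Patients whose reductions are all for LVEF keep the present path of 60, 40, 20 mg and stop. A one-level step-down after every LVEF event would also remove the conflict, but it would change the two unchanged-dose states as well. That is a clinical option for the sponsor, not a required correction.

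The cost is one sentence in two rows at the next amendment, with no change to visits or data collection. The downside is that an occasional patient already on a reduced dose stays at 20 mg or stops cobimetinib instead of receiving 40 mg.
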